**The Effect of Using Two Different Suturing
Techniques on Free Gingival Marginal Stability
after Esthetic Crown Lengthening for Treatment
of Gummy Smile
(Randomized Clinical Trial)**

Methodology

Document date: 3 /1/2020

Sample selection and assignment:

Thirty patients (26 females, 4 males), who were candidates for esthetic crown lengthening, participated in this prospective clinical trial.

The subject was recruited consecutively from the outpatient clinic of Oral Medicine, Periodontology, oral Diagnosis and Radiology Department, Faculty of Dentistry, Ain Shams University and faculty of dental medicine, Misr international University. The purpose of the study was explained to all patients and an informed consent was signed before the conduction of the study. The proposal was presented to the faculty of Dentistry Ain Shams University Research Ethics committee and was approved before starting the research ()

Patient selection:

Inclusion Criteria:

1. Patients complaining from gummy smile (altered passive eruption)
2. Age range (21-40) years.

3. Bone level is 2 mm or less from the cemento enamel junction
4. Teeth included were free from any periodontal destruction
5. Good compliance with the plaque control instructions following initial therapy.
6. Availability for follow up and maintenance program.

Exclusion criteria:

1. Presence of systemic diseases which could influence the outcome of the therapy (*American society of anesthesiologists I, ASA I*).
2. Patient suffering from periodontitis stage 4 grade C.
3. Presence of smoking habit.
4. Presence of occlusal interferences.
5. Pregnant females and lactating females. .
6. Vulnerable groups of patients (handicapped, mentally retarded and prisoners).
7. Restored teeth.

Grouping Criteria:

The study consisted of two groups the number of patient was determined by sample size calculation through G power analysis (15 patients). Patients were randomly selected using computer generated randomization (www.randomizer.org).

Group 1 (15 patients) (Periosteal suture) :

Esthetic crown lengthening procedure: internal bevel, sulcular and interdental incisions, flap elevation, bone removal then External vertical mattress suture was done (periosteal suture).

Group 2 (15 patients) (Figure of eight suture) :

Esthetic crown lengthening procedure: internal bevel, sulcular and interdental incisions, flap elevation, bone removal then modified interrupted suture was done (Figure of eight suture).

III- Assessments:

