1-Clinical parameters:

For the selected sites, the following clinical parameters were assessed preoperative (baseline) 3 and 6 months after surgical procedure.

1. Plaque index *Silness and Löe 1964*
2. Gingival Index *Löe and Silness 1963.*
3. Probing depth (PD) *Glavind and Loe, 1967*
4. Length of Attached gingiva

2-Esthetic outcome evaluation:

The following parameters were assessed 1, 3 and 6 months after surgical procedure:

- Level of the gingival margin (GM) through measurement of the crown length from the reference point in the surgical stent to the gingival margin (*Deas et al., 2004*).
- Marginal tissue contour (MTC) using root coverage esthetic score (RES) system (*Cairo et al. 2009*): Zero points = irregular gingival margin (does not follow the CEJ); 1 point =proper marginal contour/scalloped gingival margin (follows the CEJ).

- Papillary fill using classification of papillary fill (*Jemt 1997*) which it's score is as follows:
 - PIS1: entire papilla missing, lack of convexity
 - PIS 2: fills less than the interdental space, slight convexity.
 - PIS 3: fills more than half the interdental space but no complete fill
 - PIS 4: papilla fills the entire space, harmonic gingival contour
 - PIS 5: hyperplastic papilla covering too much tooth structure, irregular tissue contour
- Patient satisfaction prior surgery and 6 months post-surgery (*Silva et al., 2015*).

Patient satisfaction criteria

Prior to surgery

- How would the patient rate the gun shown when smiling, size of the upper teeth, the length of upper teeth and the width of it (way too little, too little, about enough and too much way too much)

After surgery

- Is the patient satisfied with the gingival display during talking and smiling, teeth display during

Material and Method

talking and smiling (not at all, slightly, somewhat, very and extremely).

- How was the procedure experience (much worse, worse, same as I thought, better and much better).

Presurgical therapy:

- Full Conventional periodontal treatment including supra, subgingival scaling and root planning were performed using hand scalers and curettes.
- Oral hygiene instructions(regular brushing 3 times/day, flossing and using mouthwash) were repeated until patients had achieved a proper level of oral hygiene where plaque index (PI) ≤ 1 .
- Teeth were examined for caries, periapical infection and restorative procedures in order to be treated.

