- Assessment parameters were recorded prior to surgery using UNC-15* manual probe (Hu Friedy)
- Alginate impressions were made 4 weeks following initial therapy of each maxillary arch to fabricate customized probing stents. Full-arch probing stents were made on stone casts Stents were trimmed to the height of contour, and

* PCPUNC15 Single-ended, color-coded probe. ergonomic handle. University of North Carolina, Hu Friedy, USA.

Material and Method

grooves were placed at sites to be measured with a narrow fissure bur to act as reference points for clinical parameters assessment.

(IV) Surgical procedures

Group (1)

- 1) Anesthesia (Articaine HCL 4% containing epinephrine at a concentration of 1:100,000)[†] was administrated at the selected teeth.
- 2) The tooth width to length ratio was determined according to the golden proportions (RED: The successive width proportion, when viewed from the facial aspect, should remain constant as we move posteriorly from the midline) (***Ward 2001***)
- 3) Bone sounding was done(patient was given anesthesia probing until the bone level was done using UNC-15[‡] manual probe) to determine the bone position in relevance to the CEJ position then bleeding points were done to determine the amount of the gingival tissue that was removed

[†] Artinibsa 4%cartouches de 1.8ml ,inibisa dental.

[‡] PCPUNC15 Single-ended, color-coded probe. ergonomic handle. University of North Carolina, Hu Friedy, USA.

Material and Method

- 4) Primary submarginal incision, secondary intrasulcular then tertiary incision at the papillary area were done using the surgical blade (15c)[§]
- 5) Full thickness flap reflection at the crestal bone area using mucoperiosteal ** elevator was done, while at the papillary area partial thickness flap using the surgical blade (15c)^{††} was done.
- 6) After flap reflection the supracrestal soft tissue were removed using surgical curette^{‡‡} (universal curette 2R/2L,4R/4L)
- 7) Ostectomy 3mm from the cemento enamel junction were performed using end cutting burs^{§§}. Root surfaces were scaled to remove remnants of supracrestal connective tissue fibers.
- 8) Flap was repositioned by external vertical mattress (periosteal suture) suturing technique using resorbable 5-0 vicryl sutures^{***}

[§] Trinon sterile scalpel Blades ,lot0483,Germany

^{**} Buser Periosteal handle #6, Hu- Friedy, USA.

^{††} Trinon sterile scalpel Blades ,lot0483,Germany

^{‡‡} Universal Curettes(2R/2L),(4R/4L), Hu-Friedy ,USA

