- Patients were instructed to rinse twice daily with Tantum verde[■] mouth rinse or hot saline mouthwash and to avoid mechanical plaque removal at the site of surgery
- Sutures were removed after 2 week.
- Patients were instructed not to brush for 2 weeks and not to floss the surgical area for 4 weeks.
- After 15 days patient were instructed to use modified bass technique for tooth brushing (***Carranzaa 12th edition***)

\$\$\$\$ Augmentin 1gm,Medical union pharmaceuticals(MUP) Egypt under license from ,Glaxosmithkline

***** Flagyl 500 mg, sanafi Aventis Egypt under license of sanafi Aventis French.

††††† Brufen 400mg, Al kahira pharm. and chem.Ind.Co. under license from abbott laboratories

[■]Tantum Verde Mouthwash and Gargle(Benzydamine hydrochloride 0.15g): Bottle of 125 ml, Eipico Egypt under license of A.C.R Angelini Francesco.SpA.Italy

VI-Postoperative evaluation and assessment:

Monthly recall appointments were scheduled

- The follow up period included oral examination, plaque and calculus removal when necessary
- Clinical and esthetic parameters were evaluated and scored by a separate operator at 1, 3 and 6 months postoperative the patient satisfaction was evaluated 6 months post-operative only
- All data were statistically analyzed

VII-Statistical analysis:

Statistical analysis was then performed using a commercially available software program (SPSS 18; SPSS, Chicago, IL, USA).

Values were presented as mean, standard deviation (SD), median, range and confidence intervals. Data were explored for normality using Kolmogorov-Smirnov test of normality. For parametric data, Independent t test was used for 2 group's comparisons, while ANOVA test was used to compare different observations.

Material and Method

Plaque and gingival indices and most values of difference and percent change were non-parametric and were compared using Mann Whitney U test for intergroup comparisons, while Friedman test and Wilcoxon signed Rank test were used for intragroup comparisons

Qualitative data were expressed as frequencies and percentages and were compared using Chi square test

The level of significance was set at $P \leq 0.05$.

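### No primary comparison, stability reference visit or multiplicity rule: 17 to 21 or more equal-status between-arm tests, each at P ≤ 0.05

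*Combined protocol and SAP*

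**What the plan says.** The title sets the question: "Techniques on Free Gingival Marginal Stability". Under 2-Esthetic outcome evaluation, the margin is defined by "measurement of the crown length from the reference point in the surgical stent to the gingival margin", and the schedule is "The following parameters were assessed 1, 3 and 6 months after surgical procedure". Marginal contour and papillary fill share that schedule.

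Under III- Assessments, 1-Clinical parameters, plaque index, gingival index, probing depth and attached gingiva are "assessed preoperative (baseline) 3 and 6 months after surgical procedure". Section VI differs: "Clinical and esthetic parameters were evaluated and scored by a separate operator at 1, 3 and 6 months postoperative". So a 1-month clinical visit appears in one place and not in the other.

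Under Presurgical therapy, "Assessment parameters were recorded prior to surgery" does not say which parameters are meant. The same section says "Alginate impressions were made 4 weeks following initial therapy of each maxillary arch to fabricate customized probing stents", so a stent existed from which the margin could have been read before surgery.

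Section VII gives the independent t test for parametric data, Mann-Whitney for the two indices and for changes ("most values of difference and percent change were non-parametric and were compared using Mann Whitney U test"), and chi-square for qualitative data, with one significance threshold of 0.05. It names no covariate, primary comparison or adjustment for multiple testing. It does not say which outcomes were analysed as differences or percent changes, or from which visit. Grouping Criteria attributes the 15 patients to a G power calculation but gives no outcome, effect size or power.

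**The concern.** Stability means movement of the margin after surgery. To answer the title question, a reader must know from which reading, to which visit and on which scale movement is judged. None of these is fixed, so several margin results could each be presented as the answer.

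All other outcomes stand on the same footing under the same threshold. One chance P ≤ 0.05 among them could be reported as a suture effect.

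A raw stent-to-margin level reflects tooth size, stent position and tissue excised as well as later movement. If the raw 6-month level is taken as stability, patient differences already present at the end of surgery add noise and can hide a real difference in movement.

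A smaller matter is that pre-operative probing depth and attached gingiva were collected but are not used to sharpen the comparison of the same measures at 6 months.

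**Working it through.** **The plan's own figure.** The sample size cannot be reproduced, because no inputs are given. Back-solving a two-sided t test at 0.05, 15 per arm gives 80% power only for a standardised difference of about 1.06. Nothing ties that difference to an outcome, so the calculation does not reveal a primary.

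**Number of tests.**
- III- Assessments: 4 clinical parameters × 2 post-operative visits + 3 esthetic parameters × 3 visits = 8 + 9 = 17.
- Section VI, with clinical parameters also at 1 month: 4 × 3 + 3 × 3 = 21.
- Satisfaction items, differences and percent changes are not counted.

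**Chance of at least one false positive if the arms do not differ.**
- Independent tests, 1 − 0.95^m: m = 17 gives 0.582, m = 21 gives 0.659, and m = 3 (margin level at three visits) gives 0.143.
- Correlated normal test statistics (400,000 draws; correlations assumed):

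| Correlation within / between outcomes | 17 tests | 21 tests | Margin level, 3 visits |
|---|---|---|---|
| 0.7 / 0.3 | 0.446 | 0.493 | 0.109 |
| 0.9 / 0.5 | 0.320 | 0.343 | 0.083 |

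- Margin with three levels and two differences from 1 month: 0.181 at an assumed between-visit correlation of 0.7, and 0.162 at 0.9.
- Margin with three levels, three pairwise differences and three percent changes (nine tests): about 0.20–0.21 by simulation, assuming a mean of 10 mm, a coefficient of variation of 12% and between-visit correlations of 0.5 to 0.9.

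**Which margin measure carries the stability signal.** Assume a between-arm difference in movement of 0.8 SD of movement, 15 per arm, a two-sided test, and movement independent of the position at the end of surgery. Let that position have an SD of k times the SD of movement.
- Change from an immediate post-operative reading: noncentrality 0.8/√(2/15) = 2.19, df 28, power 56.2%.
- ANCOVA on that reading: variance × 27/26, df 27, power 54.5%.
- Raw 6-month level: SD √(1 + k²), power 47.3%, 32.2% and 15.7% for k = 0.5, 1 and 2.
- Change from 1 to 6 months: let a fraction f of the movement, in mean and in variance, occur after month 1. The standardised difference is 0.8f/√f = 0.8√f, against 0.8/√(1 + k²) for the raw level. The change has more power when f > 1/(1 + k²), that is above 0.8, 0.5 or 0.2 for k = 0.5, 1 or 2.

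**Probing depth and attached gingiva.** Assume d = 0.8, one value per patient, and correlation r between the pre-operative and 6-month values. ANCOVA has variance (1 − r²) × 27/26 and df 27. Power is 58.4%, 66.8% and 82.7% for r = 0.3, 0.5 and 0.7, against 56.2% unadjusted (df 28). The two are equal at r = 0.199.

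**Holm.** With the 6-month margin set aside as primary, 16 or 20 tests remain. The smallest P value must then reach 0.05/16 = 0.0031 or 0.05/20 = 0.0025.

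**The case against.** The strongest reply is that the title makes the margin the evident main outcome, and for its level over three visits the false-positive chance is only 8–14%. The 32–49% is driven largely by plaque, gingival index, probing depth and papilla tests that nobody would take as the answer to the title question. This stands as a limit on the larger figure. It does not supply the missing visit, scale and reference, and the margin figure rises to 16–18%, or about 20%, if differences and percent changes of the margin were also tested.

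Four stronger readings are tempting, and the documents do not support them:
- *That the margin has no post-surgical reading to serve as a reference.* The 1-month reading is listed and can serve. What is missing is a reading right after suturing and a named reference visit.
- *That the plan judges stability from the raw level.* Section VII says differences were compared between arms; it does not say whether the margin was among them.
- *That no pre-operative margin reading exists.* The Presurgical therapy wording leaves this open. Such a reading would in any case mix the planned tissue removal with later movement.
- *That unadjusted tests bias the comparison.* Randomisation keeps them valid; covariates affect precision only.

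ANCOVA also has no advantage over simple change for the margin under the model above (54.5% against 56.2%), so either is acceptable.

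Finally, the document is in the past tense and already reports which values were non-parametric, so the data appear to have been examined. A primary named now may be post hoc. That limits what the fix can restore, but clear labels remain useful to readers.

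**Conclusion.** The point holds in this form. The plan leaves the title question without a designated comparison and without a reference visit for stability, and it puts 17 to 21 or more between-arm tests under one unadjusted threshold. The chance of at least one false positive is about 32–49% under assumed correlations (58–66% if independent), and 8–14% for the margin level alone. The test counts come from the document. The correlations, effect size, r, k and f are assumptions.

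No single test is invalid. The weakness lies in how the set of results can be read and selected. The unused pre-operative values are a minor loss of precision. This should be corrected in the reporting, but it does not undermine the trial.

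**What to change.** 1. **Primary.** Name one comparison, gingival margin stability at 6 months, two-sided 0.05, with a 95% CI for the between-arm difference.
   - If an immediate post-operative stent reading was recorded, use change from it or ANCOVA on it; choose one and say which. Report that reading by arm, since it is taken after suturing.
   - If not, use the within-patient change from 1 to 6 months, described as movement after month 1 that misses first-month movement. Report the 6-month level by arm as final margin position, adjusted for a pre-operative stent reading if one exists.
   - Label the primary post hoc if results have been seen.
2. **Everything else.** Either apply Holm to all other between-arm tests or report them with CIs and without significance claims, and state which. Use one scale per outcome and drop percent change as a between-arm test. Settle whether clinical parameters have a 1-month visit.
3. **Probing depth and attached gingiva.** Analyse the 6-month values by ANCOVA on the listed pre-operative values, with a rank-based version if residuals are clearly non-normal.

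**Cost.** Wording and re-analysis, with no new data. ANCOVA uses one residual degree of freedom (28 to 27) and gains nothing if r is below about 0.2. Fewer results can be called significant. Without an immediate post-operative reading, first-month movement cannot be recovered. If results were already seen, error control is not restored; the change then makes the status of each result clear.

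### The ordered five-level satisfaction answers appear to be compared by Chi square, which ignores their order and gives up power that Mann Whitney would keep at 15 per arm

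*Combined protocol and SAP*

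**What the plan says.** Under Patient satisfaction criteria, the post-surgery satisfaction items are answered on five ordered levels: "talking and smiling (not at all, slightly, somewhat, very and extremely". Procedure experience has five more: "How was the procedure experience (much worse, worse, same as I thought, better and much better". Section VI sets the timing: "the patient satisfaction was evaluated 6 months post-operative only". Each post-surgery item is therefore one ordered answer per patient at 6 months.

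The arms are "Group 1 (15 patients) (Periosteal suture") and "Group 2 (15 patients) (Figure of eight suture").

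Section VII gives Mann Whitney to a named set of variables: "Plaque and gingival indices and most values of difference and percent change were non-parametric and were compared using Mann Whitney U test". For the rest it says "Qualitative data were expressed as frequencies and percentages and were compared using Chi square test". It does not name the satisfaction or procedure-experience items, and it gives no ordinal or trend test and no fallback for small counts.

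**The concern.** Verbal answers shown as frequencies and percentages fit only the Chi square sentence. This is a reading by elimination, because the plan does not say so outright.

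Pearson Chi square gives the same result if the answer levels are shuffled. A move from *slightly* to *extremely* counts no more than a move from *slightly* to *somewhat*. It also spreads its sensitivity over up to four degrees of freedom, while the natural question (does one suture leave patients more satisfied?) concerns a single direction. With 15 patients per arm, a real shift in satisfaction is then more likely to be reported as no difference than it needs to be. These items are the trial's only patient-reported outcome.

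**Working it through.** **Inputs.** From the documents: 15 patients per arm (Grouping Criteria), five ordered levels (Patient satisfaction criteria), significance at P ≤ 0.05 (section VII). Sidedness is not stated; two-sided is assumed. Answer distributions and effect sizes are not given, so they are assumed and varied.

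**The plan's own figure.** The 15 from the G power analysis cannot be reproduced, because no effect size, SD, power or endpoint is given. For scale, 15 per arm at two-sided 0.05 and 80% power detects a standardised mean difference of (1.960 + 0.842) × √(2/15) = 1.02.

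**Sparse cells.** With equal arms, a cell's expected count is half its column total, so it is below 5 when that total is below 10. Thirty answers can fill at most two columns to 10 or more if four or five levels are used. At least 2 of 4 levels (50%) or 3 of 5 (60%) therefore have expected counts below 5. With two or three levels used, the minimum is zero. Here sparseness makes the test conservative rather than invalid.

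**Power.** The assumed baselines, lowest to highest level in %, are 20/20/20/20/20, 10/20/40/20/10, 5/10/20/35/30 and 1/2/7/30/60. A common odds ratio was applied at every cut-point, in both directions. As an example, odds ratio 4 upward from the flat baseline moves the top level from 20% (odds 0.25) to 50% (odds 1). From 60% (odds 1.5) it moves to 6/7 = 86%. There were 20,000 simulated trials per scenario, with Chi square on used levels without correction and Mann Whitney by the tie-corrected normal approximation.

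| Odds ratio | Chi square rejects | Mann Whitney rejects |
|---|---|---|
| 1 (no difference) | 2.7-4.4% | 4.6-5.3% |
| 2 | 7.9-9.4% | 14.5-18.1% |
| 3 | 15.4-19.1% | 26.1-36.8% |
| 4 | 22.4-29.6% | 35.3-53.8% |
| 6 | 32.9-47.6% | 49.1-74.5% |

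The lowest powers come from the 1/2/7/30/60 baseline shifted up, where 45-69% of tables use three levels or fewer. A second simulation, with five assumed distributions and 10,000 trials each, gave 27-30% v 50-53% at odds ratio 4 and 45-48% v 72-75% at 6. Its near-ceiling case was shifted down only, which explains its higher lower limits.

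For upward shifts, Chi square would need about 25-27 patients per arm at odds ratio 4, or 24-25 at 6, to match Mann Whitney at 15.

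**Worked table (assumed answers, lowest to highest).** One arm 1/3/5/4/2, the other 0/1/2/5/7.

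- Chi square with equal arms is Σ(a−b)²/(a+b) = 1/1 + 4/4 + 9/7 + 1/9 + 25/9 = 6.17 on 4 df, p = 0.19. All ten cells have expected counts below 5.
- Mann Whitney: column totals 1/4/7/9/9 give midranks 1, 3.5, 9, 17, 26. The second arm's rank sum is 3.5 + 18 + 85 + 182 = 288.5, against an expected 15 × 31/2 = 232.5. The tie-corrected variance is (225/12) × [31 − (60 + 336 + 720 + 720)/870] = 541.7. Hence z = 56/23.27 = 2.41 and p = 0.016 (exact form 0.017).

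**Spread without a shift.** For 5/15/60/15/5 v 20/20/20/20/20, power is 45% by Chi square and 6.5% by Mann Whitney.

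**The case against.** **The assignment to Chi square is inferred.** The plan never says which test applies to satisfaction, and *qualitative* fits the 0/1 marginal contour score well. If the answers were coded 1 to 5, they could have been ranked like the plaque and gingival indices. This stands as a limit on certainty. Chi square remains the natural reading, and the same sentence of wording closes the gap either way.

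**Chi square is not invalid here.** Its size is below 5%, so no false-positive harm arises. This stands, and the sparse-cell count adds little to the argument.

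**The benefit depends on a shift.** The documents state no directional hypothesis for satisfaction, and for a pure spread difference the ranking reverses. This stands as a real downside, although a shift is the more natural target when asking which technique satisfies patients more.

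**Part of the gap is conservatism, not lost order.** With permutation p-values for both tests, the gain stays at about 15-21 points in the three less skewed cases but falls to 2-3 points in the near-ceiling case. The claim survives, but it is weak if nearly everyone answers at the top.

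**Exact p-values could be preferred with ties and 15 per arm.** That is a legitimate choice. The tie-corrected form nevertheless holds its size (4.6-5.3%), so the preference for it is defensible.

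**Conclusion.** The concern holds, as a minor point. On the natural reading of section VII, an ordered outcome is compared by a test that discards the order. For a directional difference of odds ratio 3 to 6, that costs roughly 11 to 27 percentage points of power (26.1 − 15.4 = 10.7 at the low end, 74.5 − 47.6 = 26.9 at the high end). This rests on the assumed proportional-odds shifts and answer distributions, on two-sided testing at 0.05, and on the inference that these items fall under Chi square.

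The gain is limited: at odds ratio 4 Mann Whitney still reaches only 35-54%, because 15 per arm is small. The outcome is a supporting one, and the analysis of gingival margin level, the subject of the title, is not touched.

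**What to change.** Add one sentence to section VII: each post-surgery satisfaction item and the procedure-experience item is compared between arms by tie-corrected Mann Whitney. Keep frequencies and percentages for description.

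Name the form of the test in advance. If answers pile up at the top level and shift upward, the exact form loses most of the gain: at odds ratios 4 and 6 its power is 26% and 38%, against 35% and 49% tie-corrected and 22% and 33% for Chi square.

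No change is proposed for the marginal contour score, which is binary, or for papillary fill, whose top level (hyperplastic) is not simply better than the level below.

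The test is already in the plan, so the cost is wording, plus the loss of sensitivity to a spread-only difference. The methods text is written in the past tense. If the data have already been analysed, the Mann Whitney result must be labelled a re-analysis, since a more powerful test chosen after seeing results is a post hoc choice.
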